7. PLANNED ANALYSIS

Unless otherwise specified in this TSAP or related documents, the format for displaying analysis results will follow BI guidelines and standards.

The following descriptive statistics will be displayed in summary tables of continuous variables:

N	number of non-missing observations
Mean	arithmetic mean
SD	standard deviation
Min	minimum
Median	median
Max	maximum

For tables that are provided for continuous endpoints with some extreme data values, summary statistics such as median, quartiles and percentiles may be preferred to mean, standard deviation, minimum and maximum values.

Summaries of categorical data will include tabulations of the number of observations and the percentages of the respective treatment arm for all possible categories. Percentages will be rounded to one decimal place, unless the denominator is less than 100 in all treatment columns, in which case integer values will be displayed. A separate category for missing values will be displayed only if values of a particular variable are missing for at least one subject.

Individual values of data collected from all patients will be listed by treatment group, center, patient number and visit. These source data listings will be provided in Appendix 16.2 of the CTR.

7.1 DEMOGRAPHIC AND OTHER BASELINE CHARACTERISTICS

Descriptive statistics are planned for this section of the report. Demographics and baseline characteristics will be summarized for the TS. Data will be presented for each treatment arm and for all treated patients combined.

The summary of demographic data will include age at time of informed consent, race, ethnicity and sex.

Baseline clinical characteristics summarized will include baseline disease characteristics, including DRSS level, BCVA score, and OCT central subfield thickness (CSFT), and substance use at screening.

In addition, data related to diabetic retinopathy history will be summarized separately. The following variables will be summarized:

- Duration of diabetic retinopathy calculated as the difference between the reported onset date and the patient's date of randomization;
- N (%) of patients reporting a history of Type I diabetes mellitus;
- Duration of diabetes mellitus Type I calculated as the difference between the reported onset date and the patient's date of randomization;
- N (%) of patients reporting a history of Type II diabetes mellitus;
- Duration of diabetes mellitus Type II calculated as the difference between the reported onset date and the patient's date of randomization;
- N (%) of patients reporting a history of arterial hypertension, myocardial infarction, transient ischemic attacks, stroke and diabetic nephropathy.

7.2 CONCOMITANT DISEASES AND MEDICATION

Descriptive statistics will be provided for this section of the report based on the treated set.

Concomitant drug therapies (CT) and ophthalmic interventional drug therapies are coded according to WHO DD and will be classified according to the Anatomical Therapeutic Chemical (ATC) classification system. The third ATC level will be used to categorize CTs by therapy type. In situations where a medical product may be used for more than one equally important indication, there are often several classifications alternatives. As appropriate, patients receiving CTs with more than one possible ATC level-three category will be counted more than once; a footnote will clarify this possible double counting in tables. If a level three ATC category is not available, a lower level category may be reported. Separate summaries will be presented for concomitant drug therapies ongoing at baseline and concomitant drug therapies with start dates after date of first dose of study drug. Ophthalmic interventional drug therapies and general concomitant drug therapies will be summarized separately.

Concomitant non-drug therapies will be coded using the current version of MedDRA at the time of database lock. Ophthalmic non-drug therapies will be presented by reported term. Separate summaries will be presented for concomitant non-drug therapies ongoing at baseline and concomitant non-drug therapies with start dates after date of first dose of study drug. Ophthalmic non-drug therapies and general non-drug therapies will be summarized separately.

Concomitant medical conditions are coded similarly to AEs based on the most current MedDRA version at the time of database lock. A summary of concomitant conditions will be provided by treatment group, system organ class (SOC) and preferred term (PT).

The coding version number will be displayed as a footnote in respective outputs.

7.3 TREATMENT COMPLIANCE

Overall compliance will be calculated as the weighted average of the non-missing compliance values reported on the eCRF for each 28-day interval during the on-treatment period (Visits 3, 4 and EOT). The weighted average will be calculated as the sum of the reported compliance values multiplied by their respective interval durations in days, divided by 100. In the calculation of overall compliance, missing compliance values for a visit interval with confirmed drug administration records will be imputed as 100%. Compliance will be summarized by visit interval and overall.

The number and percentage of patients with non-missing overall treatment compliance of <80%, 80%-120%, and >120% and descriptive summaries of overall compliance will be reported.

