#### **4.1.6 Packaging, labelling, and re-supply**

The investigational products will be provided by BI or a designated Contract research organization (CRO). They will be packaged and labelled in accordance with the principles of Good Manufacturing Practice (GMP). Re-supply to the sites will be managed via an IRT system, which will also monitor expiry dates of supplies available at the sites.

All trial medication will be contained in medication boxes identified with the trial number and medication number. Each medication box will contain sufficient BI 1467335 tablets or matching placebo for 28 days treatment plus 7 days reserve.

For details of packaging and the description of the label, refer to the ISF.

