### 4.3 TREATMENT COMPLIANCE

Patients are requested to bring all remaining trial medication including empty package material with them when attending visits.

Based on tablet counts, treatment compliance will be calculated as shown in the formula below. Compliance will be verified by the Clinical Research Associate (CRA) authorised by the sponsor.

$$\text{Treatment compliance (\%)} = \frac{\text{Number of tablets actually taken} \times 100}{\text{Number of tablets which should have been taken as directed by the investigator}}$$

If the treatment compliance is not between 80-120%, site staff will explain to the patient the importance of treatment compliance.

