This interim phone call will be performed in advance to the EOT visit in order to collect AEs, changes in concomitant therapy, and to check handling of the trial drug diary. Patients should be reminded not to take medication in the morning prior to the EOT visit.

End of Treatment (EOT) Visit:

For patients who complete treatment as scheduled, the day of the EOT Visit is the last day of treatment where trial drug will be administered at the site from the kit that the patient returns to the site.

The overall duration of the anticipated treatment period (Randomization to EOT) should not be less than 84 days; therefore the EOT visit is scheduled at Day 85 with a time interval of up to +6 days at maximum.

If the trial drug intake needs to be permanently stopped during the treatment period for any reason prior to the scheduled EOT visit, including that patients are not willing to continue trial drug intake any longer, the EOT visit will be completed instead of the planned treatment period visit as soon as possible after trial drug discontinuation. In this case the patient should be asked to further attend to the follow-up visits and assessments until the end of the trial unless they withdraw consent to participate in the trial. It is important to distinguish between premature trial drug discontinuation, i.e. early discontinuation, and complete withdrawal of consent to participate in further study procedures.

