A2.9	Glomerular filtration rate (eGFR) < 60 mL/min/1.73m ² at screening or expected during trial	Exclusion criterion 10 met	None
A2.10	ALT or AST > 2x ULN or total bilirubin > 1.5x ULN	Exclusion criterion 11 met	None
A2.11	Excluded medical condition	Exclusion criteria 12, 13, 14, 15, 16 or 23 met	None
A2.12	Significant substance abuse	Exclusion criterion 17 met	None

Table 6.2: 1 Important protocol violations (cont.)

Category / Code	Description	Comment	Excluded from
	A2.13	Hypersensitivity to trial drug or allergy to fluorescein dye	Exclusion criterion 18 met
	A2.14	Major surgery performed within 12 weeks prior to randomization or planned during trial	Exclusion criterion 19 met
	A2.15	Current enrollment in, or < 30 days or 5 times half-life of the investigational drug since participating in, another investigational drug trial	Exclusion criterion 20 met
	A2.16	Previous randomization in this trial	Exclusion criterion 21 met
	A2.17	Women who are pregnant, nursing, or who plan to become pregnant during the trial	Exclusion criterion 22 met
B	Informed consent		
	B1	Informed consent not available/not done	Inclusion criterion 8 not met; informed consent date or signature missing
	B2	Informed consent given late	Study informed consent date after date of any study-related procedure; biobanking informed consent date after sample collection date; or re-consent given late.
C	Trial medication and randomisation		
C1	Incorrect trial medication taken		
	C1.1	No study medication taken	Patient randomized but no evidence of study medication taken
	C1.2	Incorrect trial medication taken	Incorrect medication taken for >20% of treatment duration or > 20% of last dose interval before primary endpoint assessment as identified after database lock by comparison of assigned drug kit number from IRT with drug kit number recorded in eCRF. [manual review]
C3	Non-compliance		
	C3.1	Non-compliance with trial medication	Mean overall treatment compliance across treatment duration for an individual <80% or >120%.
C4	Medication code broken		
	C4.1	Medication code broken at site without just cause	Medication code broken for reasons other than those documented in CTP Section 4.1.5.2. [manual review]

Table 6.2: 1 Important protocol violations (cont.)

Category / Code		Description	Comment	Excluded from
D		Concomitant medication		
	D2	Use of prohibited concomitant medication	Reported use of prohibited concomitant medications, defined in CTP Section 4.2.2.1[manual review]	PPS
F		Trial specific		

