7.7 EXTENT OF EXPOSURE

Basis for the assessment of treatment exposure will be the amount of trial medication and the duration of exposure in days calculated across the on-treatment period for each patient.

Standard summary statistics will be displayed by treatment arm. In addition, the number and percentage of patients in exposure categories defined as 0 to 6 weeks, >6 to 12 weeks will be summarized.

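### SAP 7.3 divides the day-weighted compliance sum by 100 rather than by total days, so a fully compliant 84-day patient scores 84 instead of 100%

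*SAP*

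**What the plan says.** SAP section 7.3 states the aim: "Overall compliance will be calculated as the weighted average of the non-missing compliance values reported on the eCRF for each 28-day interval", with three intervals ending at Visits 3, 4 and EOT. The calculation it then gives is "the sum of the reported compliance values multiplied by their respective interval durations in days, divided by 100". A missing interval value is set to 100% only where drug administration is confirmed by records; otherwise the interval drops out. The result is tabulated as the number and percentage of "patients with non-missing overall treatment compliance of <80%, 80%-120%, and >120" per cent.

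Protocol section 4.3 puts compliance on the percent scale: tablets actually taken, times 100, over the "Number of tablets which should have been taken as directed by the investigator". The same section treats 80% to 120% as the acceptable range.

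SAP Table 6.2:1, code C3.1, makes non-compliance an important protocol deviation, defined as "Mean overall treatment compliance across treatment duration for an individual <80% or >120" per cent. It does not cite section 7.3. The table is broken at that row in the copy reviewed, so whether C3.1 removes a patient from the PPS cannot be read.

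**The concern.** The weights are interval days, so the sum has to be divided by the total of those days to return to the percent scale. The figure of 100 looks like a percent-to-proportion conversion. Used alone, it leaves a quantity measured in days, which is then compared with percentage limits.

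Three things are at stake:

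- **The overall compliance summary and its three bands.** The score depends on how long a patient was counted as well as on how well the patient took the drug. Early discontinuers look non-compliant whatever they did while on drug. If discontinuation differs between arms, the table would show a compliance difference that need not exist.
- **The important-deviation list.** Section 7.3 holds the only definition of overall compliance in the SAP, so it is the natural source for C3.1.
- **Intervals without a value.** The divisor stays at 100 when an interval drops out, so the score falls simply because data are missing.

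**Working it through.** The SAP gives no worked value for overall compliance, so there is no figure of its own to reproduce.

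**Inputs**

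- Three intervals, nominally 28 days each, 84 days in total (SAP 7.3).
- Actual length (Protocol 6.2.2): "the EOT visit is scheduled at Day 85 with a time interval of up to +6 days at maximum". Elapsed from Day 1 this is 84 to 90 days; counted inclusively it is 85 to 91. The SAP does not say which count applies, so the range 84 to 91 is used.
- Interval compliance in percent (Protocol 4.3; imputation at 100% in SAP 7.3).
- Two tablets due per day (Protocol 4.1.1 and 4.1.4).

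**Formulas**, with c_i the compliance in percent and d_i the days of interval i:

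- As written: S = Σ(c_i × d_i) / 100
- Duration-weighted average: A = Σ(c_i × d_i) / Σd_i

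Hence S = A × T / 100 with T = Σd_i, and S equals A only if T = 100.

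**What S measures.** If 2 × d_i tablets are due in interval i, then c_i = 100 × tablets_i / (2 × d_i), and S = Σtablets_i / 2, the number of daily doses taken. Check: 54, 50 and 56 tablets over three 28-day intervals give S = 160 / 2 = 80.0, whereas A = 160 / 168 = 95.2%.

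**Results**, with the same true compliance in every interval:

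| True compliance | Counted days | Score as written | Weighted average |
|---|---|---|---|
| 100% | 84 | 84.0 | 100% |
| 100% | 85 | 85.0 | 100% |
| 100% | 91 | 91.0 | 100% |
| 96% | 84 | 80.64 | 96% |
| 95% | 84 | 79.8 | 95% |
| 90% | 84 | 75.6 | 90% |
| 88% | 91 | 80.08 | 88% |
| 87% | 91 | 79.17 | 87% |
| 100% | 56 | 56.0 | 100% |
| 100% | 42 | 42.0 | 100% |
| 100% | 28 | 28.0 | 100% |

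**Lower limit.** S reaches 80 when true compliance is 8000 / T: 95.2% for 84 days, 94.1% for 85, 88.9% for 90 and 87.9% for 91. Patients from 80% up to that value are wrongly placed below 80%. With T below 80, even 100% compliance falls there.

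**Early discontinuers.** SAP 7.7 sets "exposure categories defined as 0 to 6 weeks, >6 to 12 weeks will be summarized". Six weeks is 42 days, so full compliance in the first category scores at most 42.

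**Upper limit.** S exceeds 120 only when true compliance is above 12000 / T: 142.9% for 84 days and 131.9% for 91. Each kit holds "28 days treatment plus 7 days reserve" (Protocol 4.1.6), so three kits supply 3 × 35 = 105 daily doses. Without replacement medication the score cannot exceed 105. True compliance from three kits is at most 105 / 84 = 125.0% or 105 / 91 = 115.4%, so this end has little practical weight.

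**Alternative reading.** If compliance were held as a fraction, a perfect 84-day patient would score (3 × 1 × 28) / 100 = 0.84. That does not fit the bands either.

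**The case against.** The best defence is that the intention is plain. Section 7.3 twice calls the quantity a weighted average, imputes at 100% and reports on a percent scale, so a programmer might well have divided by total days. By-interval figures are reported alongside, and perfect intervals next to an overall value of 84 would be noticed. The trial is exploratory with no confirmatory testing, and the affected output is descriptive. All of this limits the consequences. It does not make the formula right: the SAP is the specification that programs are checked against, and no other place in the documents gives the correct divisor.

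Three narrower objections have some force:

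- **C3.1 has its own wording.** A mean across treatment duration could be read as already normalised, and the 80% and 120% limits are also the protocol's general ones. The effect on C3.1 is therefore probable, not shown.
- **A missing interval is unlikely in a completer.** Dosing at Visits 2a, 3, 4a and EOT is supervised and recorded in the eCRF (Protocol 4.1.4.1), so imputation at 100% would usually apply. The score of 56 for a perfect completer needs one 28-day interval to be both missing and not imputed, which should be uncommon.
- **The dose-count identity is conditional.** It needs tablets due to equal two per counted day, while Protocol 4.3 refers to what the investigator directed. The scores and thresholds in the working do not depend on this condition.

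**Conclusion.** The concern holds. As written, section 7.3 yields counted days scaled by compliance instead of a percentage. Over the scheduled 84 to 91 days it understates compliance by a factor of 0.84 to 0.91. True compliance from 80% up to 95.2% (84 days) or 87.9% (91 days) is misclassified as below 80%, and so is every fully compliant patient with fewer than 80 counted days. A perfect 84-day patient scores 84 and still lands in the middle band, so the error would not reveal itself in the best compliers' category.

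The conclusion assumes that the sentence is applied literally and that compliance values are in percent, as both documents indicate. How many patients would be misclassified cannot be worked out from the documents. The overall summary and its bands are wrong as specified; C3.1 is probably wrong. No PPS effect is claimed, because the exclusion entry cannot be read. Compliance by visit interval, the primary endpoint on the TS and the main DRSS analysis on the FAS are not affected. It should be fixed, but it does not touch the trial's main results.

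**What to change.** Replace the calculation sentence in SAP 7.3 with: overall compliance (%) = Σ(interval compliance % × interval days) / Σ(interval days), both sums taken over the intervals with a reported or imputed compliance value. This returns 100% for any fully compliant patient, whatever the duration or the number of intervals counted. In Table 6.2:1, state that C3.1 uses this value.

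The cost is one SAP sentence, one cross-reference and one program line before database lock. No new data are needed and patients are not affected.

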##### **4.1.4.1 Trial medication administration at the study site**

At Visits 2a, 3, 4a and EOT the administration of trial medication is done at the study site under the supervision of the investigator or qualified site staff. Two tablets of the trial drug will be administered with a glass of water after predose blood sampling. The actual visit date and time of trial drug administration at the visit will be recorded in the eCRF at each visit.

At Visits 2a, 3 and 4a, new trial medication boxes will be used for administration of the morning dose at the clinical site and will be dispensed for home administration. At EOT visit trial medication will be taken from the box that the patient returns to the site.

Patients who erroneously take the morning dose of trial medication before coming to the clinic at visits 3 and EOT (with scheduled PK samples) should have the visit rescheduled as soon as possible, ideally on the following day.

The site staff will instruct and remind the patients:

- how to fill in the trial medication diary and to bring the diary to the next visit
- not to take their trial medication at the morning of the next visit as they will be dosed while at the sites after blood samples are taken (as described in [Section 6.2.2](#))
- to bring all trial medication blisters within the box (regardless of whether empty or not) back to the investigational site

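### SAP 7.3 sets missing tablet-count intervals to 100% on an undefined condition, and its divisor of 100 does not yield a percentage

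*SAP*

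**What the plan says.** SAP 7.3 makes three statements about overall compliance, one after the other.

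1. Averaging rule: "Overall compliance will be calculated as the weighted average of the non-missing compliance values reported on the eCRF for each 28-day interval" (Visits 3, 4 and EOT).
2. Formula: the average is the "sum of the reported compliance values multiplied by their respective interval durations in days, divided by 100".
3. Imputation: in calculating the overall figure, "missing compliance values for a visit interval with confirmed drug administration records will be imputed as 100"%.

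The next paragraph of SAP 7.3 reports "The number and percentage of patients with non-missing overall treatment compliance of <80%, 80%-120%, and >120"%. The same limits define important deviation C3.1 in SAP Table 6.2: 1: "Mean overall treatment compliance across treatment duration for an individual <80% or >120"%.

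The measurement comes from Protocol 4.3: "Based on tablet counts, treatment compliance will be calculated as shown in the formula below". The count depends on patients bringing back their remaining tablets and packaging.

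**The concern.** A tablet count measures how much drug was taken over a whole interval. The imputation replaces a missing count with a full-compliance value on the strength of records that may show only that some drug was taken. The SAP does not say which records qualify, or how many are needed.

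It also does not say whether the imputation overrides the non-missing average or works as an exception to it. Two programmers could therefore produce different overall values, and different C3.1 flags, for the same patient.

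What is at stake is how far the compliance table and the C3.1 listing can be trusted. A reader uses both to judge whether an absent drug effect, or an absent safety signal, could reflect poor intake. A rule that lifts patients over the 80% limit because their counts are missing weakens that use. The formula has its own fault: its result is not on the scale of the 80% and 120% limits.

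**Working it through.** The documents give no worked compliance figure, so there is none to reproduce.

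**Inputs**
- Three intervals of 28 days, 84 days in total (SAP 7.3; Protocol 6.2.2). The EOT window of +6 days allows 28/28/34, or 90 days.
- Limits of 80% and 120% (SAP 7.3; Table 6.2: 1, C3.1).
- Site doses at Visits 2a, 3, 4a and EOT: "The actual visit date and time of trial drug administration at the visit will be recorded in the eCRF at each visit" (Protocol 4.1.4.1).
- Home doses: patients keep a diary of every dose (Protocol 4.1.4.2), but only the 3 days before each visit are entered in the eCRF (Protocol 6.2.2).

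**Step 1: what could meet the imputation condition.** The doses at Visits 2a, 3 and 4a come from the newly dispensed box, so each interval normally opens with one recorded dose. Adding the 3 days before the next visit gives 1 + 3 = 4 recorded doses in a 28-day interval (4/28 = 14%). The last interval also has the EOT dose. On a loose reading, these few records are enough to assign 100%.

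**Step 2: true weighted average**, Σ(compliance × days) / Σ(days), over 28/28/28 days. Let t be the observed mean.
- One interval imputed: (2t + 100)/3 ≥ 80 gives t ≥ 70.
- Two intervals imputed: (t + 200)/3 ≥ 80 gives t ≥ 40.

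| Observed values | Non-missing average | With 100% imputed |
|---|---|---|
| 75 / missing / 75 | 75.0 (flagged) | 83.3 (not flagged) |
| 70 / 70 / missing | 70.0 (flagged) | 80.0 (not flagged) |
| 60 / 60 / missing | 60.0 (flagged) | 73.3 (flagged) |
| 40 / missing / missing | 40.0 (flagged) | 80.0 (not flagged) |
| all missing | missing | 100.0 |

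For 28/28/34 days with the later interval(s) imputed, the lower bounds fall to (7200 − 3400)/56 = 67.9% and (7200 − 6200)/28 = 35.7%.

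To illustrate the distance from the truth, take 70/70/missing. If actual intake in the missing interval was 0, 50 or 70%, true overall compliance is 46.7, 63.3 or 70.0%, against 80.0% as imputed.

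**Step 3: the formula as written**, Σ(compliance × days) / 100, over 28/28/28 days.
- Full compliance: 100 × 84 / 100 = 84, not 100 (90 for a 90-day course).
- A fully reported 84-day patient reaches 80 only at 8000/84 = 95.2% compliance.
- An interval left out is in effect counted as zero: 70/70/missing gives (1960 + 1960)/100 = 39.2.
- With imputation, 75/100/75 gives (2100 + 2800 + 2100)/100 = 70. Both 70/70/100 and 40/100/100 give 67.2. All three stay below 80.

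The 70% and 40% bounds of Step 2 therefore require the true weighted average that the SAP names, not the formula that it then writes.

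**The case against.** **Is there a contradiction?** A reader might infer that the non-missing average and the imputation contradict each other. The text does not support that. The imputation is conditional on dosing records and can be read as an exception, with other missing intervals left out. The SAP also expects some overall values to stay missing, because it tabulates only non-missing ones. What stands is that the order is unstated, an imputed value is not a reported one, and the condition is undefined.

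**Are non-compliers hidden?** Not fully. The imputation applies only to the overall figure. Compliance is also summarized by visit interval (SAP 7.3), individual values are listed (SAP 7), and important deviations are reviewed before database lock (SAP 6.2). Low observed intervals remain visible. What is lost is the overall category and the automatic flag.

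**Is the bias always upward?** No. Where observed values exceed 100%, imputation pulls the result down: 125/125/missing becomes (125 + 125 + 100)/3 = 116.7. The rule raises the figure whenever true compliance in the missing interval is below 100%.

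**Do missing counts signal poor adherence?** That is plausible but unproven. The documents give no rate or cause of missing counts. The 2020 site disruption and phone visits described in SAP 4 are another possible cause. The condition might also be applied strictly, using the full diary, but the SAP does not say so.

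**Is the alternative better?** Averaging only the counted intervals assumes that uncounted ones resemble them, and two missing intervals leave 84 days judged on 28. This is a fair limit, and it is why incomplete counts need their own category.

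**Conclusion.** The point holds as a minor defect in the compliance calculation, in two parts.

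First, an undefined condition permits a best-case value for a missing count. On a true weighted average over three equal intervals, which is the apparent intent, observed compliance of 70 to <80% (one imputed) or 40 to <80% (two imputed) leaves the <80% category and escapes C3.1. A patient with no counts at all could be reported as 100%. This assumes that a few recorded doses satisfy the condition.

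Second, and regardless of any imputation, the divisor is wrong. As written, it would place fully reported 84-day patients with compliance from 80% to just over 95% below the limit.

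The reach is the compliance table and C3.1. A reader might go on to infer damage to the trial's main results, but the documents do not support this. The primary endpoint and the other safety analyses use the treated set, which has no compliance condition (SAP 6.3), and the trial is exploratory with no confirmatory testing (Protocol 7.2). The per-protocol repeat of the DRSS analysis would be touched only if C3.1 excludes patients from that set. In the copy of Table 6.2: 1 available here, the exclusion entry for C3.1 cannot be read, so this is not claimed.

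**What to change.** Rewrite the calculation paragraph of SAP 7.3:

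- **Main calculation:** sum compliance × days over the intervals that have a tablet count, and divide by the summed days of those same intervals. This also corrects the divisor.
- **Incomplete counts:** show patients with one or more uncounted intervals as a separate category in the compliance table.
- **Sensitivity summary only:** report overall compliance and C3.1 with 100% imputed, after defining which records, and how many, count as confirming drug administration in an interval.

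The cost is a few SAP sentences and no new data. A few more patients may appear as non-compliant or incomplete. The main figure will still rest on the assumption that uncounted intervals resemble counted ones, and this should be stated beside the table.
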